8.2 Protocol compliance

The main factor determining protocol compliance will be appropriate timing of enrolling the patients early in pregnancy to allow for sufficient exposure to the treatment and follow-up during gestation. Loss of patients or missing ANC visits will reduce treatment compliance as well as outcome detection.

8.3 Unblinding

The need for unblinding should be extremely rare as the trial intervention is not associated with severe side effects and it will not delay or prevent standard management of the patient in the case of a complication such as renal calculus. If the woman develops pre-eclampsia or eclampsia, she will be treated according to routine treatment protocols regardless of the supplementation status. If, however, unblinding is needed for any reason the trial coordinator in Geneva will be contacted to reveal the treatment.

8.4 Data processing

Data entry and checking will be continuous and queries will be followed vigorously to ensure that clarification will be without delay.

8.5 Analysis plan

An analysis plan has been finalised before recruitment starts. A draft layout of the proposed analysis plan is presented in Appendix 2 in dummy tables.

Principal analyses will be on an intention-to-treat principle with comparisons made between calcium and placebo for primary and secondary outcomes. Stratification will be made for

time gestational age of entry into the trial by each woman and by baseline calcium intake level of populations served by the hospitals. These hospitals will be classified as serving a population of very low (< 200mg), low (200-400mg), or medium (400-599mg) calcium intake before initiation of the trial. An exploratory analysis will be conducted for the hypothesis that the effect will be larger among women who started treatment before 16th week of pregnancy and among populations with the lowest baseline calcium intake.

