3.5.2 Randomization

Simple randomization will be conducted independently for each study site by the HRP/RHR statistical unit at WHO headquarters and provided to the pharmaceutical manufacturer.

The random allocation sequence will be generated using computer-generated random numbers. Randomization will be to the two arms of the trial and stratified by country. Blocking with randomly varying groups of 6-8 will be used to restrict randomization within the strata (country) (SAS Software, Copyright© 1989, 1994 SAS Institute, Inc., N.C., USA).

Random allocation technique consists of allocating consecutively numbered treatment boxes for each woman, including in each box seven independent bottles, each of them with tablets for four weeks of treatment. Each bottle contains 100 tablets. Therefore each subject will have seven bottles with the same randomization number. Treatment boxes will be kept at the clinic. Bottles will be provided consecutively as needed every month after randomization. When the woman comes for antenatal care, she will return the used bottle from the previous month and will be given the next month's bottle from her box. She will return the bottle after 4 weeks, regardless of whether she finished the tablets or not. Each bottle is numbered from 1 to 7 within the box and should be used sequentially.

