3.6.3 Anthropometry

Anthropometry (weight and height) of the mother during the first antenatal visit, and birth weight of her baby will be routinely collected. The methodology will be standardized and careful quality control of equipment instituted. Women wearing light clothes will be weighed on a calibrated scale. Height will be measured without shoes.

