10.2.2 Administrative

- Preparation of a trial newsletter.
- Assistance with the organization of trial-related meetings including travel arrangements.
- Maintaining a mailing list of trial contacts (collaborators, trial steering and data monitoring committee members).
- Posting, photocopying, faxing.

11 Links with other projects

There will be eight centres in seven countries. All of these, Argentina, Colombia, Egypt, India, Peru, South Africa and Vietnam, are experienced in calcium supplementation trials or in other WHO multicentre collaborations. Argentina has also participated in the Collaborative Eclampsia Trial, the Misoprostol trial and the Antenatal Care trial, also funded by WHO. Egypt, South Africa and Vietnam participated in the WHO Misoprostol trial.

This trial is linked to the Maternal Health Research Programme of HRP/RHR for the prevention of leading causes of maternal mortality which has been approved by the Maternal Health Research Strategic Group and the Scientific and Technical Advisory Group (STAG) of HRP/RHR. Furthermore, this trial is linked to another smaller RCT being conducted in the Gambia by the University of Cambridge and the UK MRC exploring in a detailed manner the mechanisms by which high calcium intake to calcium deficient women can influence blood pressure during pregnancy. The endpoints in this latter trial are physiological measurements and blood pressure and the trial is not designed to test the hypothesis of prevention of pre-eclampsia.

12 Main problems anticipated

Most anticipated problems have been resolved during the preparation of the protocol based on the experience of previous trials. The main challenge remains, however, the follow-up of large numbers of women enrolling early in pregnancy in developing country settings.

13 Expected outcomes of the study

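### Section 3.5.2 describes two incompatible randomisation schemes, and the analysis strata in 8.5 do not include whichever stratum was used

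*Protocol*

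**What the plan says.** **Randomisation (3.5.2).** The section opens with "Simple randomization will be conducted independently for each study site". The next paragraph says "Randomization will be to the two arms of the trial and stratified by country", and then "Blocking with randomly varying groups of 6-8 will be used to restrict randomization within the strata (country"). Section 11 adds: "There will be eight centres in seven countries".

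**Principal analysis (8.5).** "Principal analyses will be on an intention-to-treat principle with comparisons made between calcium and placebo for primary and secondary outcomes". Stratification is then to be made for "gestational age of entry into the trial by each woman" and "by baseline calcium intake level of populations served by the hospitals", with hospitals placed in three intake classes. An exploratory hypothesis about early starters and the lowest-intake populations follows. The note under the outcome tables in Appendix 2 lists the same two factors for stratified analyses. Section 8.5 also says that an analysis plan was finalised before recruitment; it is not among the documents at hand.

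**Interim test (8.6).** After 4500 subjects, the difference between the two groups' pre-eclampsia proportions is tested two-sided at 0.01. No stratum is mentioned.

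**The concern.** There are two linked problems.

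First, a reader cannot tell from 3.5.2 which allocation list was made. Simple randomisation puts no restriction on the running balance between arms, whereas permuted blocks do. *Per site* and *per country* also differ wherever a country has more than one centre. The list goes to the manufacturer and becomes consecutively numbered boxes held at clinics, so the description should match one real list.

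Second, where the protocol names its analysis strata, it names two factors that are not the randomisation stratum and omits the one that is. It also leaves open whether those two factors adjust the principal comparison or only define subgroups. If allocation is balanced by blocking within a stratum and the test takes no account of it, the test uses a variance slightly too large for the design. What is at stake is a little precision and a clear link between design and analysis.

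**Working it through.** **1. The two schemes side by side.**

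| | First description | Second description |
|---|---|---|
| Restriction | none (*simple*) | blocks of 6-8 |
| Unit | study site (8, if site means centre) | country (7) |

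The practical difference is visible. With 8500 women in eight equal centres (equal size assumed), each has 8500/8 ≈ 1062 women. Under simple randomisation the arm difference in a centre has SD √1062 ≈ 33 women. With complete blocks it is zero, and with a last incomplete block of 8 it is at most 4. Also, 1:1 blocks must be even, so 6-8 can only mean 6 or 8.

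**2. Randomisation stratum against analysis strata.** Randomisation: site or country. Analysis (8.5, Appendix 2): gestational age at entry and hospital calcium class. Calcium class may capture part of the site differences, but it has only three levels and is not the blocked factor.

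**3. What omitting the stratum costs, if allocation is blocked within country.**

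Inputs from 3.5.1: N = 8500, 1:1, 4% against 2.8% (RR 0.70). From 8.6: final α = 0.05; two-sided is stated only for the interim test and is assumed here for the final one. Also assumed: seven equal countries (4250/7 ≈ 607 women per arm each), with placebo rates of either
- (a) 2, 2.5, 3.5, 4, 4.5, 5.5, 6%, or
- (b) 1, 1.5, 2, 3, 4, 6.5, 10%.

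Both have mean p̄ = 4%. The protocol gives no figures by country.

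*Reference power.* With a common 4% rate, the pooled two-proportion test at 8500 has 86.3% power. The protocol states 80%, which by this formula needs 7160 women. That mismatch is a separate matter and does not affect this comparison.

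*Size of the unstratified test.* Let B be the mean of (p_k − p̄)². The unstratified variance is too large by the factor R = p̄(1−p̄)/[p̄(1−p̄) − B], and the true size is 2[1 − Φ(1.96√R)]. Here p̄(1−p̄) = 0.04 × 0.96 = 0.0384.
- (a) B = 0.0013/7 = 0.000186; B/0.0384 = 0.48%; R = 1.0049; size 0.049.
- (b) B = 0.00625/7 = 0.000893; B/0.0384 = 2.3%; R = 1.024; size 0.047.

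*Power, unstratified.* Difference 0.04 − 0.028 = 0.012. Pooled SE = √(2 × 0.034 × 0.966/4250) = 0.003931. Numerator 0.012 − 1.96 × 0.003931 = 0.004295. Divide by the true SE under blocking:
- (a) 0.004295/0.003921 = 1.095, power 86.3%.
- (b) 0.004295/0.003889 = 1.104, power 86.5%.

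*Power, Mantel-Haenszel test stratified by country.* z = [Σ(n_k/2)(0.3p_k) − 1.96√V0]/√V1, where n_k is women per arm in country k, and V0 and V1 are the stratum variances summed under the null and the alternative. The sum is 303.6 × 0.3 × 0.28 = 25.5.
- (a) √V0 = 8.337, √V1 = 8.332; z = 1.099, power 86.4%.
- (b) √V0 = 8.272, √V1 = 8.265; z = 1.124, power 86.9%.

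*Check by 40,000 simulated trials per scenario.* (a) power 86.6% unstratified, 86.7% stratified; size 0.048 and 0.049. (b) power 86.7% and 87.1%; size 0.047 and 0.049.

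Section 3.5.1 puts 4% at the lower end of the candidate centres. A set that respects this, such as 4, 4, 5, 5, 6, 7, 8% (assumed), has mean 5.57%, B = 0.000196 and B/[p̄(1−p̄)] = 0.000196/0.0526 ≈ 0.4%, slightly below case (a). So the lower end of the range is the more plausible.

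If allocation had truly been simple, the unstratified test would have its nominal size. Even this small effect therefore depends on which sentence in 3.5.2 is right.

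**The case against.** The strongest reply is that 8.5 fixes no test, model or covariate set and points to a separate analysis plan, which is where stratification of the test would normally be settled. That stands against one tempting inference: a reader might conclude that the principal comparison is unadjusted and ignores the randomisation strata. The protocol does not say so. It says only which strata it names, and the randomisation stratum is not among them. The interim wording in 8.6 likewise does not exclude a stratified test.

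A reader might also infer that baseline prognostic information is ignored. That is not supported either: gestational age at entry is a woman-level baseline value and is named. Maternal weight and height are collected ("Anthropometry (weight and height) of the mother during the first antenatal visit"), and entry blood pressure is needed for eligibility, but not adjusting for them is no error. The documents give no basis for a figure on what such adjustment would gain. Section 2.1 says that screening tests for risk have not been successful, and 3.3.2 excludes women with raised blood pressure, which narrows its range at entry.

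It can also be said that the second paragraph of 3.5.2 is specific enough to show the intended scheme, and that the protocol uses *centre* and *country* loosely: the recruitment table in Appendix 2 is headed by centre but lists seven countries. That makes the contradiction easy to repair. It does not remove it, because section 11 counts eight centres.

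Finally, pooling countries with different rates is not a bias when each is randomised 1:1. That is correct.

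**Conclusion.** The contradiction in 3.5.2 is plain on the page and needs correction. The mismatch between the randomisation stratum and the named analysis strata is also real, as a statement about what the protocol names. Whether the analysis as performed would leave the stratum out cannot be told from this document.

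The numerical consequence is small: about 0.1 to 0.4 points of power at 8500 women, and a test size of 0.047-0.049 instead of nearer 0.05. These figures rest on assumed country rates, equal country sizes, blocking within country and a two-sided final test. The direction is conservative. There is no type I error inflation and no bias in an unstratified comparison, so the validity of the trial is not in question. The case for the change is that it costs almost nothing and ties the analysis to the design.

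**What to change.** - **3.5.2:** delete *Simple*; name the one stratum actually used, site or country; give the block sizes as 6 or 8. Which stratum it is should follow the list that was generated.
- **8.5 and 8.6:** state that the principal and interim comparisons of pre-eclampsia are stratified by that factor, for example with a Mantel-Haenszel relative risk and its test.
- **8.5 and Appendix 2:** say whether gestational age at entry and hospital calcium class are adjustment factors or subgroup factors.
- **Optional:** a supporting model with entry blood pressure and body mass index, without a claimed gain.

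The cost is a few sentences and routine analysis code. The stratum is known for every woman from her allocation, so no new data are needed. If the separate analysis plan already stratifies by the randomisation factor, only the protocol wording has to be aligned with it.

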8.6 Data Safety and Monitoring Committee

A Data Safety and Monitoring Committee (DSMC) with no direct involvement in the trial will be appointed. [name] of South Africa will chair it. The role of DSMC will be to deal with any ethical issues that may arise while the trial is in progress, and to scrutinise an interim analysis. Reporting and handling of adverse events will be in accordance with the GCP guidelines.

The DSMC will be asked to give advice regarding the trial if they have proof beyond doubt of an important advantage or disadvantage for one of the treatment groups, and they consider that the results are likely to affect clinical practice. Based on previous trials it seems unlikely that a major disadvantage will be apparent.

An interim analysis is going to be suggested to the DSMC to be conducted after the completion of the first 4500 subjects. If the difference between the proportions of occurrence of pre-eclampsia in the two groups is significant in a two-sided test at the level $\alpha=0.01$ then the trial will be stopped prematurely. The adjustment for repeated testing at the final analysis will then be negligible, leaving a significance level of practically $\alpha=0.05$.^{41,42}

9 Duration of the project.

It is anticipated that the whole project can be completed in approximately three years if the time scale of appendix 5 is adhered to. The recruitment will begin in November 2001.

10 Project management

The trial coordination and management, including data management and analysis, will be by the Special Programme of Research, Development and Research Training in Human Reproduction (HRP) of the Department of Reproductive Health and Research at WHO headquarters. [name], [name] [name], and [name] will be the trial coordinators in Geneva, assisted by other staff of HRP/RHR as required (Trial Coordination Unit). The trial management will include coordination and execution of the following activities which require administrative and clinical research input.

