2.4 Justification for a new trial

It seems clear that there is promising evidence of a protective effect of calcium supplementation during pregnancy on pre-eclampsia when provided to women with deficient calcium intake, and that evidence is biologically plausible. There is, however, strong support for the concept that definitive confirmation is needed in the context of an adequately sized and methodologically sound randomized controlled trial targeted specifically to a population with low calcium intake, i.e. the most likely to benefit from such an intervention. This is because most of the trials in low calcium intake populations were small and prone to exaggerate the protective effect, with the largest of them having wide confidence intervals, including one (the null hypothesis). Furthermore, as the implementation of daily calcium supplementation early in pregnancy will need substantial efforts, including early antenatal care and community organization, which are mostly not readily available in developing countries, the avoidance of implementing an intervention without compelling evidence is crucial.

The need for a definitive trial has been raised on several occasions recently. The Cochrane review concluded, "*Further randomised trials should concentrate on women at high risk of gestational hypertension, and communities with low dietary calcium intake.*"⁹ A commentary on the randomized controlled trials available concluded that "*Until a large trial*

of calcium supplementation in women at high risk for toxemia or with poor dietary calcium intake is completed, calcium should not be used for primary or secondary prevention." ²⁸

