3.5 Methods

3.5.1 Sample size and power considerations

The total minimum sample size was determined to be 8500 women, with half allocated to receive calcium supplements and the other half to receive placebo tablets. This sample size is sufficient to obtain 80% power to detect a 30% reduction in the rate of pre-eclampsia in the calcium group (2.8%), as compared with the placebo group rate of 4%. This rate in the placebo group is based on data obtained from one of the populations considered for the study, with HRP/RHR/WHO supported population based data collection system. This rate is at the lower end of the range from other candidate centres and gives the sample size calculation a conservative approach. An even more conservative estimation is a reduction in the rate of pre-eclampsia from 3.5% in the placebo to 2.45% in the calcium group, which requires a total of 9000 women. A total of 4500 women will be sufficient to show a reduction from 4% to 2.40% or a RR of 0.60. This latter sample size will be used as the milestone for the first interim analysis.

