10.2 Conduct of the trial

10.2.1 Coordination activities

- Trial staff during the course of the trial will conduct at least two site visits to each centre to monitor trial progress. The first is expected after 3 months of recruitment.
- Communication with local investigators to monitor trial progress.
- Communication with the data monitoring and steering committees of the trial.
- Weekly meetings of the Trial Coordination Unit and data management group (HRS/HRP/RHR, Geneva).
- Data management and statistical analysis.

- Data entry.
- Data validation and production of queries based on a pre-set of cut off points for data verification.
- Update of the master file using batches of new data or corrections coming from validation checks and/or answers to queries.
- Correspondence between HRS/HRP/RHR and the centres related to queries.
- Monitoring reports: recruitment, adverse events, loss to follow-up, completeness of data for main outcomes.
- Statistical analysis: interim analyses, final analysis.

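### Section 8.6 calls the final-analysis adjustment negligible, but a 0.01 interim look followed by a 0.05 final test gives an overall type I error of 5.42%

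*Protocol*

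**What the plan says.** Three parts of the protocol bear on this.

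- **Interim rule (8.6, last paragraph).** "An interim analysis is going to be suggested to the DSMC to be conducted after the completion of the first 4500 subjects". If the difference in pre-eclampsia "in the two groups is significant in a two-sided test at the level" 0.01, the trial is to be stopped early. The paragraph ends: "The adjustment for repeated testing at the final analysis will then be negligible, leaving a significance level of practically" 0.05.
- **DSMC remit (8.6, the paragraph before).** The committee is to give advice "if they have proof beyond doubt of an important advantage or disadvantage for one of the treatment groups", provided it also thinks the results likely to change practice.
- **Number of looks.** Section 8.6 describes one. Section 3.5.1 says of the 4500 figure: "This latter sample size will be used as the milestone for the first interim analysis". The task list in 10.2.1 has "Statistical analysis: interim analyses, final analysis".

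**The concern.** The protocol fixes both test levels and asserts what follows from them, so the claim can be checked and is not something left to a statistical analysis plan. An interim level of 0.01 at about half the data is not extreme enough to be ignored at the end. If the final test is run at 0.05 on the strength of this sentence, the trial's primary maternal comparison has a higher false-positive rate than stated. A final p-value between about 0.0456 and 0.05 would be declared significant although the 5% error rate had already been used up.

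Two matters of wording affect how the rule is applied. The number of looks is described differently in three places. The DSMC is also given an advisory standard in one paragraph and a rule that stops the trial on a single p-value in the next, and nothing says how the two relate.

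**Working it through.** **Inputs**
- Interim after 4500 women, two-sided 0.01, so c1 = 2.576 (8.6).
- Final test at two-sided 0.05, so c2 = 1.960 (8.6).
- Total 8500, allocated 1:1, with 9000 as the more conservative alternative (3.5.1).
- Design effect 4% v 2.8%, relative risk 0.70 (3.5.1).

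**Information fraction.** Taking information as proportional to women completed, t = 4500/8500 = 0.529, or 4500/9000 = 0.50. Under the null hypothesis the interim and final statistics Z1 and Z2 are bivariate normal with correlation √t, which is 0.728 at N = 8500.

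**The protocol's figure.** The final test alone has error 0.05. Adding the interim look:

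overall error = 1 − P(|Z1| < c1 and |Z2| < c2) = 0.05 + P(|Z1| ≥ c1 and |Z2| < c2)

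The last term is the chance of stopping at the interim in a trial that would not have been significant at the end. Numerical integration gives:

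| Interim level | N = 8500 | N = 9000 |
|---|---|---|
| 0.01 | 0.0542 | 0.0546 |
| 0.001 | 0.0502 | 0.0502 |

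At N = 8500 and 0.01 the extra term is 0.0542 − 0.05 = 0.0042. So 0.05 is not reproduced at the 0.01 level; at 0.001 it very nearly is.

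**Check by simulation.** Two million binomial trials with 4% in both arms (2250 per arm at the interim, 4250 at the end) gave an overall error of 0.0540. The interim test alone rejected in 0.0098 and the final test alone in 0.0498.

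**Sensitivity to timing.** With levels 0.01 and 0.05, the overall error is 0.0567 at t = 0.3, 0.0557 at 0.4, 0.0546 at 0.5, 0.0534 at 0.6 and 0.0522 at 0.7. It exceeds 0.05 throughout.

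**Final level that restores 5%.** Solving for the final level with the interim kept at 0.01 gives 0.0456 (|Z2| ≥ 1.999) at N = 8500 and 0.0452 (|Z2| ≥ 2.003) at N = 9000.

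**Power.** For 4% v 2.8% with 4250 per arm (normal approximation, no losses), the final test alone has power 86.3% at 0.05 and 85.4% at 0.0456, a loss of 0.9 points. By the same formula, the total needed for 80% power rises from 7160 to 7362. Both are below 8500.

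**The case against.** The best defence is that the sentence is hedged. It says practically 0.05, the excess is 0.42 percentage points (about 8% in relative terms), and the critical value moves only from 1.96 to 2.00. That stands, and it limits the weight of the point. It does not make the sentence right. On either reading, as the overall error or as the nominal level for the final test, 0.05 is not the figure that belongs with a 0.01 interim level.

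The paragraph on the 0.01 rule can fairly be read as the working form of the general DSMC remit, and the analysis is only to be suggested to the committee. The protocol does not say so, however, and a duty to advise on two judgements is not the same as a stop triggered by one p-value. A linking sentence is needed. A reader might infer that the advisory standard demands a stricter boundary, but the text does not support that. The boundary, and whether it binds, are for the sponsor and the DSMC to decide.

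Two stronger readings are tempting.

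- **Several looks at 0.01.** The wording in 3.5.1 and 10.2.1 could suggest repeated looks and a larger inflation. No second look, timing or boundary is given anywhere, so any figure for it would rest on invented looks.
- **An exaggerated estimate after early stopping.** Section 2.4 calls most earlier trials in low-intake populations "small and prone to exaggerate the protective effect", and one might fault the 0.01 rule for inviting the same. That remark concerns small trials. A look at 4500 women is larger than the biggest earlier trial described (4336, section 2.2.1). Nor does the argument favour a stricter boundary as such. In simulations at 4% v 2.8%, the median observed relative risk among stopped trials is about 0.60 with the 0.01 rule and about 0.55 with a 0.001 rule, though stops are rarer (14% v 36%). Changing the final level leaves it as it is.

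**Conclusion.** The point holds as a modest correction and should be fixed. The overall two-sided type I error is 5.42% at N = 8500 and 5.46% at N = 9000, against a stated value of practically 5%.

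The result assumes one look at 4500 women, information proportional to women completed, and every interim crossing counted as a positive result that ends the trial, as 8.6 says. If the DSMC sometimes continued after a crossing and only the final test then counted, the error would lie between 5% and 5.42%. This is one reason why the status of the rule should be clear.

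The documents do not support calling this a serious loss of error control. The differences over the number of looks and the DSMC standard are matters of wording to reconcile, not evidence of a further inflation.

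**What to change.** In 8.6, if the 0.01 interim level is kept, replace the sentence on negligible adjustment with an explicit final two-sided level: about 0.0456 at 8500 women or 0.0452 at 9000, to be recomputed from the information fraction actually reached. If the sponsor and DSMC instead settle on a much stricter interim level, the present sentence can stay; 0.001 gives 5.02%.

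Make 3.5.1 and 10.2.1 refer to a single interim analysis, as in 8.6. Add a sentence to 8.6 saying how the 0.01 rule relates to the advisory standard in the paragraph before it, and whether a crossing stops the trial or leads to a recommendation.

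The cost is a text change and, with the 0.0456 level, about 0.9 points of power at a relative risk of 0.70. No more women are needed for the 80% power stated. The change should be made before the interim data are seen, so that it cannot be thought data-driven.
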